3.2.2. Subject Population Analyzed

The following analysis populations are defined for this study:

- Full Analysis Set (FAS): All randomized patients who have received at least 1 injection of Study Drug (ISIS 757456 or Placebo) and who have at least 1 post-Baseline primary efficacy measurements.
- Per Protocol Set (PPS): All FAS patients who received at least 10 of the 12 doses of Study Drug, did not alter antihypertensive medications during the Treatment Period and prior to Study Day 85, and have no significant protocol deviations that would be expected to affect efficacy assessment. Significant protocol deviations are defined as those deviations from the protocol likely to impact the perceived efficacy and/or safety of study treatments, for example, other antihypertensive medication usage compliance during the study. After all data are entered, reviewed, and queried, the database is closed and sent to clinical group for review and identification of significant protocol deviations before unblinding.
- Safety Set: All patients who are randomized and receive at least 1 dose of Study Drug.
- Pharmacokinetics (PK) Set: All patients who are randomized and receive at least 1 dose of ISIS 757456 and have at least 1 evaluable PK sample.

In addition to the above analysis sets, it is recognized that some data displays will be provided for the number of patients in "All Screened", "Screening Failures" and "All Randomized" but no data analysis will be executed in these populations. A by-patient listing based on all randomized will be provided.

3.2.3. Handling of Missing Data

Unless otherwise specified, missing values will not be imputed.

Patients with missing data for a scheduled assessment time point will be excluded from the summary for that time point.

Number of patients with missing data and missing data related to COVID-19 public health emergency may be provided.

3.2.4. Disposition of Subjects

The number of patients screened, screen failures, the number and percentage of patients randomized, dosed, completed the study treatment, discontinued from treatment early and reason, completed post-treatment follow-up, and discontinued from post-treatment follow-up and reason will be tabulated by treatment group.

A by-patient listing will also be provided.

Additional by-patient listing will be provided to describe screen failures, treatment/post-treatment follow-up termination information related COVID-19 public health emergency.

3.2.5. Demographic and Baseline Characteristics

Demographic and Baseline characteristics (e.g., age, gender, ethnicity, race, cardiovascular disease (CVD) risk factors, tobacco/nicotine use, number of antihypertensive medications received, diuretic use (Y/N), CVD history, diabetic status, weight, height, BMI) will be summarized using descriptive statistics by treatment group.

Additionally, the following additional baseline characteristics will be summarized:

- Age (yrs): $< 65, \ge 65$
- BMI (Kg/m²): $< 30, \ge 30$
- eGFR (mL/min/1,73 m²): \geq 60, < 60
- heart rate
- Antihypertensive medications received by category (RAS inhibitor, beta-blocker, calcium channel blocker, diuretic, alpha-1 blocker, centrally acting sympatholytic agent, vasodilators, aldosterone antagonists)
- \geq 3 anti-HTN med with diuretic
- Number anti-HTN medications 3, 4, \geq 5
- SBP and DBP (mmHg) at baseline
- 24 hr ABPM SBP at baseline >130 SBP
- Daytime ABPM SBP at baseline > 135
- Plasma AGT
- HbA1c

- eGFR
- urinary albumin/creatinine ratio (UACR): normal: < 30 mg/g was considered normal; micro-albuminuria: 30-300 mg/g; macro-albuminuria: > 300 mg/g
- CV Risk

For race summary, if multiple races are recorded in the database, then 'Multiple Race' will be used in the summary table. The listing will display the specific race values.

BMI will be computed using the formula:

BMI = (weight in kilograms) / [screening height in cm / 100]²

Listing of medical history will be provided.

3.2.6. Protocol Deviations

Protocol deviations will be classified to major or minor based on the study protocol deviation process plan. Protocol deviations will be provided in the data listings. Additional tables may be provided to summarize the protocol deviations related to COVID-19 public health emergency.

A listing of all patients affected by the COVID-19 public health emergency related study disruption by subject number identifier and by investigational site, and a description of how the individual's participation was altered will be provided.

3.2.7. Stratification, Subsets, and Covariates

Eligible Patients will be stratified on Screening eGFR result of < 60 or ≥ 60 mL/min/1.73 m². In the case of errors in stratification, the analyses should be based on the actual stratification, regardless of IRT entry.

The following patient demographic and baseline characteristics may be considered as additional covariates in the comparison statistical modeling for exploratory analysis purposes:

- Age group (< 65 years vs. ≥ 65 years)
- Race (Caucasian vs non-Caucasian)
- Gender
- Obesity status
- Number of antihypertensive medications received
- Diabetic status
- UACR categories
- Two or more CV risk factors
- 24 hr ABPM SBP > 130 mmHg
- Chronic kidney disease status defined by eGFR (> 90 mL/min, 60-90 mL/min, and 45-59 mL/min)

3.2.8. Scoring of Questionnaires

EuroQoL-5 Dimensional 5-level Questionnaire (EQ-5D-5L)

EQ-5D-5L is a standardized measure of health status developed by the EuroQoL Group to provide a simple, generic measure of health for clinical and economic appraisal. The EQ-5D-5L consists of the EQ-5D-5L descriptive system and the EQ visual analog scale (VAS).

The EQ-5D-5L descriptive system comprises five dimensions (mobility, self-care, usual activities, pain/discomfort and anxiety/depression), and the response to each dimension is scored as: 1 = no problems/pain/anxious, 2 = slight problems/pain/anxious, 3 = moderate problems/pain/anxious, 4 = severe problems/pain/anxious, 5 = unable/extreme. Lower score indicates worsening of QoL.

The EQ VAS is used as a quantitative measure of health outcome as judged by the individual respondent. The EQ VAS records a self-rating of health status on a vertical VAS anchored at 100 (best imaginable health state) at the top and 0 (worst imaginable health state) at the bottom.

Additionally, the EQ-5D health state index score reflects how good or bad a health state is according to the preferences of the general population of a country/region will be derived and summarized. If any of five dimensions is missing, then the index value will be set as missing. The details of EQ-5D health state index score derivation algorithm is described in Appendix 1.

Patient Global Impression

Patient Global Impression of Severity (PGI-S) is a single-item scale instrument asking patients to rate the severity of their health condition on a scale of (1) none, (2) mild, (3) moderate, (4) severe, (5) very severe.

Patient Global Impression of Change (PGI-C) is a single-item scale, which aims to evaluate all aspects of patients' health and determine if there has been an improvement or not in the patients' overall change in health condition. Patients rate their change as (1) much better, (2) a little better, (3) no change, (4) a little worse, (5) much worse.

Power Over Pressure - Hypertension Specific Questionnaire (POP-HSQ)

The POP-HSQ (Schmider, et. al 2017) comprising questionnaire A and questionnaire B (what symptoms have you experienced in the last 4 weeks). In questionnaire A, patients rate their health state in part 1 to part 4 and their blood pressure management and impact in part 5 to part 7. In questionnaire B, patients provide the experienced symptoms' frequency and intensity.

Short Form (SF) -12

The SF-12 comprising 12 items that yield 8 healthy domains profile of physical and mental well-being. These 8 domains are: health domains: physical functioning (PF), role physical (RP), bodily pain (BP), general health (GH), vitality (VT), social functioning (SF), role emotional (RE), and mental health (MH). Each health domain score contributes to the physical component summery (PCS, including PF, RP, GH and BP) and a mental component summary (MCS, including MH, RE, SF, and VT). Other measures can be derived from SF-12 data, including SF-6D preference-based utility index and the medical expenditure prediction to help understand the economic impact of a patient's condition and treatment. The norm-based score for each domain and components will be calculated using Optum's SF36v2/SF-12v2 scoring software

operated by Ionis data management function personal. Higher scores are associated with a better quality of life (QOL).

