3.5. Exploratory Analyses

The exploratory efficacy analyses will be conducted using statistical methods described in Section 3.2.1. ANCOVA model will be used for continuous endpoints, logistic regression model will be used for dichotomous endpoints using PPS and FAS.

- Comparison of absolute levels, change and percent change from baseline to each scheduled post-Baseline visit in angiotensin II, renin (Plasma renin activity [PRA]; direct renin), and urinary AGT will be conducted between each ISIS 757456-treated group and pooled-placebo group in the PPS and FAS.
- Comparison of absolute scores, change from baseline to each scheduled post-Baseline visit in SF-12 scores (8 domains, PCS, and MCS), and EQ-5D-5L (5 dimensions, VAS, and index score) will be conducted between each ISIS 757456-treated group and pooled-placebo group.

- Proportion of non-worsening from baseline to each scheduled post-Baseline PGI-C and PGI-S will be compared between each ISIS 757456-treated group and pooled-placebo group. PGI-C will be categorized by non-worsening and worsening, where non-worsening includes categories of "Much better", "A little better" and "No change". PGI-S will be categorized by non-worsening and worsening, where non-worsening defined as ≥ 0 point improvement in the change from baseline score. The adjusted odds ratio (each ISIS 757456-treated dose group vs. pooled-placebo group) with 95% CI from logistic regression model will be provided.
- Comparison of change from Baseline to Study Day 85 in daytime SBP and DBP from 24 hr ABPM will be conducted between each ISIS 757456-treated group and pooled-placebo group
- Comparison of change from Baseline to Study Day 85 in nighttime SBP and DBP from 24 hr ABPM will be conducted between each ISIS 757456-treated group and pooled-placebo group
- Comparison of change from Baseline to Day 85 in eGFR will be conducted between each ISIS 757456-treated group and pooled-placebo group
- Comparison of change from Baseline to Day 85 in UACR will be conducted between each ISIS 757456-treated group and pooled-placebo group
- Primary endpoint, selective secondary and exploratory endpoints will be also analyzed using a sub-population of patients with Baseline 24 hr ABPM SBP > 130
- POP-HSQ scores will be listed.

Additional POP-HSQ summaries and analysis will be conducted, details are described in POP-HSQ SAP. Other exploratory PK endpoints will be further described in the Section 3.6.

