APPENDIX 1. EQ-5D HEALTH STATE INDEX SCORE DERIVATION ALGORITHM

To derive this index value, the response of each dimension will be first translated into a weight based on the value sets issued by EuroQoL group (see table x). The index value then can be calculated as **1- sum of weights from these 5 dimensions' response**. The possible best value is 1 for both regions and the possible worst value is -0.285 for UK region and -0.573 for US region. If there is a missing response from a dimension, then the index value will not be calculated and be treated as missing. For this study, all the other non-US counties will utilize UK county weight instead. The display of the index value is with 3 digits of decimal points.

Table 1: Weight of EQ-5D-5L Response by Region

				EQ-5D-5L Dimension		
Region	Response	Mobility	Self- Care	Usual Activities	Pain/ Discomfort	Anxiety/ Depression
UK	1) No problem	0	0	0	0	0
(16/11/2020)	2) Slight problem	0.058	0.05	0.05	0.063	0.078
	3) Moderate problems	0.076	0.08	0.063	0.084	0.104
	4) Severe problems	0.207	0.164	0.162	0.276	0.285
	5) Unable to	0.274	0.203	0.184	0.335	0.289
US	1) No problem	0	0	0	0	0
(16/11/2020)	2) Slight problem	0.096	0.089	0.068	0.06	0.057
	3) Moderate problems	0.122	0.107	0.101	0.098	0.123
	4) Severe problems	0.237	0.22	0.255	0.318	0.299
	5) Unable to	0.322	0.261	0.255	0.414	0.321

Sources: https://euroqol.org/support/tools/analysis-tools/index-value-set-calculators/

Version:	1
Version Date:	18 Aug 2022
Title:

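### SAP Section 3.2.8 states the direction of the EQ-5D-5L dimension scores backwards, so a worsening would be read as an improvement

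*Combined protocol and SAP*

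**What the plan says.** SAP Section 3.2.8 (Scoring of Questionnaires) describes three parts of the EQ-5D-5L.

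- **Five dimensions.** The coding begins "the response to each dimension is scored as: 1 = no problems/pain/anxious, 2 = slight problems/pain/anxious" and ends "4 = severe problems/pain/anxious, 5 = unable/extreme". The sentence that follows, and closes the same paragraph, is "Lower score indicates worsening of QoL".
- **VAS.** A separate paragraph describes a scale "anchored at 100 (best imaginable health state) at the top and 0 (worst imaginable health state) at the bottom".
- **Index.** It is introduced after the VAS. Appendix 1 derives it as 1 minus the "sum of weights from these 5 dimensions' response" and adds that "the possible worst value is -0.285 for UK region and -0.573 for US region".

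SAP Section 3.5 (Exploratory Analyses) uses all three parts. A comparison of absolute scores and change from baseline in "EQ-5D-5L (5 dimensions, VAS, and index score) will be conducted" between each active dose group and pooled placebo, at each scheduled post-baseline visit.

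**The concern.** The coding and the direction sentence cannot both be right. If 1 is the best level and 5 the worst, a falling score is an improvement. The direction sentence comes before the VAS and the index are introduced, so it can only refer to the 1-to-5 dimension scores.

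It also sets the dimensions against the rest of the instrument. Lower is worse holds for the VAS and the index, but not for the dimensions. An analyst or medical writer who follows the SAP would report a positive mean change in, say, pain/discomfort as a gain for the drug, while the index from the same responses fell. What is at stake is the reported direction of benefit or harm for five outcomes.

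**Working it through.** **Inputs**

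- Dimension coding and direction sentence: SAP Section 3.2.8.
- Index formula, best and worst values, and weights: SAP Appendix 1 and its Table 1.
- Outcomes compared: SAP Section 3.5.
- Assessment days: protocol Appendix A, which shows the EQ-5D-5L on Days 1, 43, 85 and 106.

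**Step 1. Reproduce the SAP's own worst index values.** Index = 1 − sum of the five weights. With every dimension at level 5, in the order mobility, self-care, usual activities, pain/discomfort, anxiety/depression:

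- UK: 1 − (0.274 + 0.203 + 0.184 + 0.335 + 0.289) = 1 − 1.285 = −0.285
- US: 1 − (0.322 + 0.261 + 0.255 + 0.414 + 0.321) = 1 − 1.573 = −0.573

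Both match the stated values. With every dimension at level 1, all weights are 0 and the index is 1, the stated best value.

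**Step 2. Move all five dimensions through the levels together.**

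| Level of all five dimensions | Index, UK | Index, US |
|---|---|---|
| 1 | 1 | 1 |
| 2 | 0.701 | 0.630 |
| 3 | 0.593 | 0.449 |
| 4 | −0.094 | −0.329 |
| 5 | −0.285 | −0.573 |

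The index falls at every step up in the dimension score.

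**Step 3. Check each dimension separately.** In all 10 columns (5 dimensions × 2 regions) the weight never decreases as the level rises. The only tie is US usual activities, 0.255 at both levels 4 and 5. A higher dimension score is therefore never better under the SAP's own weights.

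**Step 4. Apply the direction sentence to one case.** A patient's mobility goes from 1 to 5, a change of +4.

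- Appendix 1: the index falls by 0.274 (UK) or 0.322 (US), a deterioration.
- Direction sentence: lower is worse, so +4 is an improvement.

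**Step 5. Count what is affected.** The instrument yields 5 dimensions + VAS + index = 7 outcomes, of which 5 carry the wrong direction. Days 43, 85 and 106 are post-baseline, so change from baseline gives 5 dimensions × 3 visits × 2 dose comparisons = 30 comparisons in each analysis set. Section 3.5 calls for both the PPS and the FAS.

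**The case against.** The strongest reply is that the sentence enters no calculation. The comparisons use ANCOVA on the scores as coded, so the least squares means, differences, confidence intervals and p-values are the same with or without it. That stands: the error affects only how the sign is read.

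Three further points limit its importance.

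- The SAP defines no improvement or worsening category for the EQ-5D-5L; Section 3.5 does so only for the PGI-C and PGI-S. No derived variable in the plan inherits the error. The nearest exception is the rule in Section 3.2.1 that takes the worst of several results under one visit label. It applies only to categorical variables, and the change analysis treats the dimensions as continuous.
- The level labels immediately before the sentence, and the weights in Appendix 1, let a careful reader see the mistake.
- SAP Sections 1.3.4 and 3.5 class these outcomes as exploratory, and they lie outside the testing sequence in Section 3.4.2.

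These points bear on how much the error matters, not on whether it is one. Section 3.2.8 is where the SAP sets the reading of each questionnaire. It gives a direction sentence of the same kind for the SF-12, and that one is correct. Neither document corrects the EQ-5D-5L sentence elsewhere.

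**Conclusion.** The sentence is wrong as written. It contradicts the coding in its own paragraph and the weights in Appendix 1, which reproduce the SAP's best and worst index values exactly. Read literally, it reverses the interpretation of 5 of the 7 EQ-5D-5L outcomes, in absolute score and in change from baseline, at all three post-baseline assessments.

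The consequence is confined to interpretation of exploratory outcomes. No estimate or p-value changes, the VAS and index derivations are sound, and the primary and key secondary results are untouched. The conclusion assumes that the sentence refers to the dimension scores, which its position supports. It needs no figure from outside the documents. The correction should be made because the error is plain and could put the wrong sign on reported results.

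**What to change.** In SAP Section 3.2.8, replace the direction sentence with: *For each of the five dimensions, a higher score indicates worse quality of life; for the VAS and the index score, a higher score indicates better quality of life.*

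Then check the table shells, footnotes and any improvement labels, none of which are in the documents reviewed, against the corrected rule. The cost is one SAP sentence and a short check of the output templates. No data collection, derivation or model changes.

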3.3. Primary Analysis

3.3.1. Primary Efficacy Analysis

The primary analysis will be the comparison of change from Baseline to Study Day 85 (Study Week 13) in seated automated office SBP between each ISIS 757456 treatment dose group and pooled placebo group in the PPS. The data will be analyzed as described in Section 3.2.1. Least square mean (LSM) estimated treatment difference with 95% CI and p value will be provided. Additional MMRM analysis will be conducted to assess the treatment effect.

Additional covariates, such as baseline characteristics, may be considered, in the comparison statistical modeling for exploratory analyses.

Additional analysis summary based on the FAS will also be provided.

3.3.2. Sample Size consideration

Approximately 150 patients will be stratified and randomized to 1 of 2 dose cohorts in 1:1 ratio (Cohort A or Cohort B). Within each dose cohort, patients will be further randomized to receive ISIS 757456 or placebo in a 2:1 ratio.

With the assumptions of mean seated automated office SBP reduction difference of 8 mmHg between an ISIS treated group and pooled placebo with the common standard deviation of 13 mmHg, there are at least 86 eligible patients (n = 43 for an ISIS 757456 treated group and n = 43 for pooled placebo) are needed to provide approximate 80% of power to demonstrate the mean difference between an ISIS treated group and pooled placebo by ANCOVA with the two-sided significant level of 0.05. Additional patients are included while considering an estimated approximate 10% drop-out rate.

The overall type I error rate is controlled at 0.1 level, two-sided.

3.4. Secondary Efficacy Analyses

3.4.1. Secondary Efficacy Endpoints

The secondary efficacy analyses will be performed using statistical methods described in Section 3.2.1. ANCOVA model will be used for continuous endpoints, logistic regression model will be used for dichotomous endpoints. Secondary endpoints include:

- 1. Comparison of percent change from baseline to Study Day 85 in AGT between an ISIS 757456-treated group and pooled-placebo in the PPS
- 2. Comparison of change from baseline to Study Day 85 in SBP from 24-hrs mean ABPM between an ISIS 757456-treated group and pooled-placebo in the PPS
- 3. Comparison of proportion of patients reaching the goals of seated automated office SBP \leq 140 mmHg and DBP \leq 90 mmHg at Study Day 85 between an ISIS 757456-treated group and pooled-placebo in the PPS, excluding patients with baseline SBP \leq 140 mmHg

- 4. Comparison of absolute value, change and percent change from Baseline to each scheduled post-Baseline visit in plasma AGT between each ISIS 757456-treated group and pooled-placebo group in PPS and FAS
- 5. Comparison of change from Baseline to Study Day 85 in SBP and DBP from 24 hr mean ABPM between each ISIS 757456-treated group and pooled-placebo group in the PPS and FAS
- 6. Comparison of patient incidence in reaching the goals of seated automated office SBP ≤ 140 mmHg, DBP ≤ 90 mmHg, and both for each scheduled, post-Baseline visit between each ISIS 757456-treated group and pooled-placebo group in PPS and FAS, excluding patients with Baseline SBP ≤ 140 mmHg
- 7. Comparison of patient incidence in reaching the goals of seated automated office SBP \leq 130 mmHg, DBP \leq 80 mmHg, and both for each scheduled, post-Baseline visit between each ISIS 757456-treated group and pooled-placebo group in PPS and FAS
- 8. Comparison of change from Baseline to each scheduled post-Baseline visit in seated automated office SBP between each ISIS 757456-treated group and pooled-placebo group in PPS and FAS
- 9. Comparison of change from Baseline to each scheduled post-Baseline visit in seated automated office DBP between each ISIS 757456-treated group and pooled-placebo group in PPS and FAS

Figures contain the summary (mean with standard error of mean) by scheduled visit overtime based on PPS will be provided. Spaghetti plots demonstrating each individual's efficacy assessment over time by treatment group will be provided.

3.4.2. Multiplicity

The multiplicity of primary and the first three secondary endpoints will be controlled by using sequential (closed) testing strategy in the following testing sequence for interim analysis (if applicable) and final analysis, which is also illustrated in Figure 1 below.

- Comparison of change from baseline to Study Day 85 in in seated automated office SBP between an ISIS 757456-treated group and pooled-placebo in the PPS (primary)
- Comparison of percent change from baseline to Study Day 85 in AGT between an ISIS 757456-treated group and pooled-placebo in the PPS (secondary 1)
- Comparison of change from baseline to Study Day 85 in SBP from 24-hrs mean ABPM between an ISIS 757456-treated group and pooled-placebo in the PPS (secondary 2)
- Comparison of portion of patients reaching the goals of seated automated office SBP ≤ 140 mmHg and DBP ≤ 90 mmHg at Study Day 85 between an ISIS 757456-treated group and pooled-placebo in the PPS, excluding patients with baseline SBP ≤ 140 mmHg (secondary 3)

[figure not shown]

Figure 1: Testing Strategy illustration

In each dose cohort, testing of secondary endpoints will be performed only if the treatment comparison of the primary endpoint is statistically significant. All comparisons between treated group and the pooled placebo for secondary endpoints will be considered as exploratory analyses if the primary endpoint is not statistically significant (p > 0.05, or 0.049 if interim analysis is conducted). If a secondary efficacy endpoint in the sequence is not statistically significant, then the subsequent endpoints outcomes will be considered as exploratory.

